#### 5.2.7 Unscheduled Visits

Additional visits can be performed as appropriate and at the discretion of the investigator.

## 5.3 STUDY VISITS FOR PART 1 CYCLE 2

Cycle 2 visits and procedures are similar to Cycle 1, although no PK/PD measurements will be made unless specifically requested by Investigator. Refer to Table 6.3 for Cycle 2 assessments and procedures. Bone Marrow aspirates will be obtained at Cycle 1, Day 22 and every 2 cycles thereafter.

## 5.4 DESCRIPTION OF STUDY VISIT FOR PART 1 CYCLE 3 AND EACH SUBSEQUENT CYCLE OF PART 1

Cycle 3 and subsequent cycles have one scheduled visit per cycle. No PK/PD measurements will be made unless specifically requested by Investigator. Refer to Table 6.3 for Cycle 3 assessments and procedures.

#### 5.4.1 Cycle 3 and Subsequent Cycles Visit (Day 1 ± 1 of each cycle)

The following procedures will be performed at Cycle 3 and Subsequent Cycles Visit:

- Review medical history
- Record medications including start/stop dates, indication, dose and frequency taken since previous visit.
- Perform and record targeted physical examination as appropriate.
- Assess and record performance status (ECOG).
- Measure weight in kg.
- Record vital signs. Measure body temperature, systolic / diastolic BP and pulse rate.
- Perform ECG if appropriate (Patients with a normal ECG during Cycle 1 need not have repeat ECGs during subsequent cycles).
- Collect blood samples for blood chemistries, hematology and creatinine clearance.
- Collect urine samples for urinalysis.
- Perform urine pregnancy test for female patients who are not postmenopausal or surgically sterile. If urine test positive, test, collect blood for a serum pregnancy test.
- Assess and record disease status (every 2 cycles).
- Assess and record AEs.
- Obtain all unused study drug from patient.
- Assess study drug compliance by reviewing pill count.
- Bone marrow aspirate and/or biopsy. Peripheral, Geimsa and Iron stained slides will be collected with each bone marrow aspirate or biopsy. Following Cycles 1 and 2, Day 22 bone marrow aspirates will be collected only every other cycle, i.e., Cycles 4, 6, etc.

- Bone marrow cytogenetics in accordance with local pathology requirements. (Cytogenetics would preferably include at least 20 clones).
- Dispense BVD-523 for 21 days ±4 days of Cycle. Extra doses may be dispensed at the Investigator's discretion to insure continuous dosing.

# 5.5 DESCRIPTION OF STUDY VISITS FOR PART 2

Study procedures for Part 2 will be the same as those for Part 1. If clinical experience gained in Part 1 requires significant deviations in Part 2 from the procedures in Part 1, these changes will be addressed in a protocol amendment.

# 6 METHODS OF ASSESSMENT AND CRITERIA FOR EVALUATION

All trial data will be recorded on the electronic case report forms (eCRFs) (TEMPOTM). Photographs will be taken in the event a patient experiences a rash, and the photos will be uploaded into the eCRF. Blood and biopsy specimens will be sent to a third party laboratory vendor for analysis.

## 6.1 DEMOGRAPHIC DATA

At Visit 1 (Screening), patient demographic data will be collected. These include date of birth, age, gender, race, ethnicity, AML or MDS subtype and molecular abnormalities (when available).

## 6.2 MEDICAL HISTORY

At Visit 1 (Screening), a complete medical history will be obtained from each patient. For female patients of child-bearing potential, the date of the last menstrual period will be noted. Smoking history and prior cancer therapy will be recorded. Data will be reviewed at Visit 2 (Baseline) and updated at subsequent visits.

## 6.3 CONCOMITANT MEDICATIONS

A detailed history of medications, including prior anti-cancer therapies, and procedures will be documented for each patient at Visit 1 (Screening) and Visit 2 (Baseline). Concomitant medications (especially changes in medication, including any anti-cancer therapies) will be documented for each patient at each scheduled visit. Necessary supportive care such as anti-emetics and anti-diarrheals, etc., will be allowed. Medications which are known to be strong inhibitors of CYP3A4, CYP2D6, and CYP1A2, or strong inducers of CYP3A4, are not permitted during the study (for list of non-permitted drugs, see Appendix 1).

Hydroxyurea will be allowed for all subjects during Cycle 1 of treatment unless subject does not meet inclusion criterion for hydroxyurea use based on kinetics of leukemia. After Cycle 1, hydroxyurea will not be allowed for any subject on study.

## 6.4 PHYSICAL EXAMINATION

- Height in centimeters (cm) will be measured at Visit 1 (Screening).
- Body weight in kilogram (kg) will be measured at screening and at the beginning of each cycle.

- Body temperature will be measured at each visit.
- Systolic and diastolic BP and pulse rate will be measured at each visit after the patient has been in a supine position for 5 minutes. Blood pressure should be assessed on the same arm during the study.

Full physical examination evaluations at screening should include general appearance, skin, neck, eyes, ears, nose, throat, lungs, heart, abdomen, back, lymph nodes, extremities, and neurological examinations. Subsequent targeted physical exams should include body systems as appropriate.

Information about the physical examination must be present in the source documentation at the study site. The result of the physical examination prior to the start of study drug must be included in the Relevant Medical History/Current Medical Conditions Case Report Form. Clinically relevant findings made after the start of study drug, which meet the definition of an adverse event, must be recorded on the Adverse Event Case Report Form.

## 6.5 SAFETY ASSESSMENTS

Safety evaluations will be conducted at baseline, on Days 1, 8, 15, 22, 29, 36, 43, and, in patients who continue treatment, every 3 weeks or if clinically indicated thereafter. These evaluations will include a targeted physical examination, electrocardiography in subjects where clinically indicated and clinical laboratory studies. An ophthalmologic assessment will be conducted at baseline, at the end of study and at other visits by an ophthalmologist if clinically indicated.

The following clinical laboratory tests will be performed:

- **Hematology** (blood sample: EDTA) hemoglobin, hematocrit, white blood cells (WBC) count with differential, red blood cells (RBC) count, and platelet count.
- **Blood Chemistry** (blood sample: serum) albumin, alkaline phosphatase (ALP), total bilirubin, calcium, chloride, creatinine, glucose, inorganic phosphorus, potassium, total protein, alanine aminotransferase (ALT), aspartate aminotransferase (AST), sodium, blood urea nitrogen (BUN) uric acid, cholesterol and triglycerides (at screening and first day of Cycle 1).
- If the total bilirubin concentration is increased above 1.5 times the upper normal limit, total bilirubin should be differentiated into the direct and indirect reacting bilirubin.
- Urinalysis specific gravity, pH; semi-quantitative "dipstick" evaluation of glucose, protein, bilirubin, ketones, leukocytes, and blood and a microscopic examination including RBC, WBC and casts will be performed if the dipstick is abnormal.

Blood chemistry will be analyzed at each trial center by a certified laboratory and a report of the laboratory values will be sent to the trial center. The investigator or designee will review the laboratory report within 24 hours (except during clinic holidays, when review will be performed within 72 hours) after receipt of the results and assess the clinical significance of all abnormal values. Results must be reviewed prior to dosing and appropriate action taken for any clinically significant abnormal values. Values will be documented on the laboratory report until stabilized, or the laboratory value returns to a clinically acceptable range (regardless of relationship to study medication) or baseline. Any laboratory value that remains abnormal at the end-of-study (EOS) and that is considered clinically significant will be followed according to

accepted medical standards for up to 30 days or until resolution of the abnormality or return to baseline.

Ophthalmologic examinations include best-corrected visual acuity, visual field examination intraocular pressure, external eye examination, and dilated fundoscopy. For additional details refer to study manual. Note: any patient experiencing vision changes must stop taking BVD-523 and have an ophthalmic evaluation. Study drug may be re-started when symptoms resolve.

Toxicity will assessed using the National Cancer Institute Common Terminology Criteria for Adverse Events, Version 4.03.

## 6.6 PHARMACOKINETICS

Please refer to Section 6.9.

#### 6.7 PHARMACODYNAMICS

Multiple biomarkers intended to demonstrate inhibition of the molecular target and mechanism of action will be investigated, including pRSK and total RSK. Additional biomarkers, including PBMCs, and DNA sequence analysis may be identified and measured as appropriate by collection of whole blood prior to dosing initiation and after drug levels have reached steady-state.

Leukemic cell genotyping by DNA analysis may be performed to identify somatic alterations, relying on either available stored samples or freshly collected samples. Additional blood and/or bone marrow aspirate samples may also be collected to determine *ex vivo* BVD-523 sensitivity on leukemic cells by collection of whole blood prior to dosing initiation and after drug levels have reached steady-state.

## 6.8 EFFICACY

All responses will be documented. The following is a summary of the response criteria; the detailed criteria based on the published references will be used for analysis.

**MDS** – The response criterion for evaluation of MDS is based on the International Working Group (IWG) criteria published in 2006 (2).

#### Table 6.1Table 3 from IWG 2006 MDS Response Criteria

•							
Complete Response (CR): the following for 4 weeks							
Peripheral: Marrow:	normal peripheral counts with persistent granulocyte count $\ge 1.0 \times 10^{9}$ /L, platelet count $\ge 100 \times 10^{9}$ /L normal bone marrow with persistent marrow blasts $\le 5\%$ ; persistent dysplasia will be noted						
Partial Res	ponse (PR): the f	ollowing for 4 weeks					
Peripheral: Marrow:	Peripheral: normal peripheral counts with granulocyte count ≥ 1.0 X 10  /L and platelet count ≥ 100 X 10  /L Marrow: normal bone marrow with marrow blasts > 5% but were reduced by 50% or more						
Marrow Co	Marrow Complete Response (mCR): the following for 4 weeks						
Reduction of	bone marrow blasts	to ≤ 5% without normaliz	ation of peripheral counts				
Hematolog	ical Improvement	: (HI): lasts at least 8	weeks*				
Erythroid Response (HI-E): Major Response: hemoglobin increase ≥ 1.5 g/dL or RBC transfusi independence							
Platelet Response (HI-P): Major Response: absolute increase of platelet count from <20 to > 20 : 10  /L and by at least 100%, or if more than 20 X 10  /L and by at least 30 X 10  /L							
Neutrophil Response (HI-N): Major Response: granulocyte increase ≥ 100%, and by an absolute in ≥ 0.5 X 10  /L							
*Abnormal base	line counts were the av	/erages of at least two mea:	surements over at least one week prior to therapy, not influenced				

\*Abnormal baseline counts were the averages of at least two measurements over at least one week prior to therapy, not influenced by transfusions.

#### Reference: (2).

Please note that all other responses are collected as "Less than PR" within the eCRF.

AML – The response criteria for AML will be based on modified recommendation of the International Working Group (IWG) published in 2003 (1). Information regarding transfusion dependence will be noted as a visit assessment and space provided in the eCRF.

Table 6.2	Table 4 from IWG 2003 AML Response Criteria
-----------	---

Response	Peripheral Blood	Bone Marrow
CR	ANC > 1.0 x $10^9$ /L, Platelets $\ge 100 \times 10^9$ /L, independence from red cell and platelet transfusions over the past week	$\leq$ 5% blasts
CRp	ANC > 1.0 x $10^9$ /L, Platelets < 100 x $10^9$ /L, independence from red cell transfusions over the past week	$\leq$ 5% blasts
Cri	$ANC < 1.0 \text{ x } 10^9/L$	$\leq$ 5% blasts
PR	ANC > 1.0 x $10^{9}$ /L, Platelets $\ge 100 \text{ x } 10^{9}$ /L	Decrease of $\geq$ 50% in blasts to level of 5% to 25%

ANC = absolute neutrophil count; CR=complete remission; CRp=complete remission with incomplete platelet recovery; Cri=CR with incomplete blood count recovery; PR=partial remission. Reference (1).

Please note that all other responses are collected as "Less than PR" within the eCRF.

## 6.9 PHARMACOKINETIC PROCEDURES

### 6.9.1 Blood Sampling and Processing

Samples for PK analysis of BVD-523 and selected metabolites will be obtained from all patients during their first cycle of treatment (Cycle 1). PK samples may also be obtained from patients at unscheduled times or intervals if deemed scientifically or clinically justified at the Investigator's discretion.

At Visit 2 (Baseline), blood samples will be collected prior to dosing, and then at 0.5, 1, 2, 4, 6, 8, and  $12 \pm 2$  hours post-dose after the administration of the first dose of the first cycle. At Day 22 (Visit 5; at steady-state), blood samples will be collected prior to dosing and then, 0.5, 1, 2, 4, 6, 8, and  $12 \pm 2$  hours post-dose. Steady state refers to patients who have received at least 5 days, or 10 consecutive doses, of investigational product. If patient is not at steady state at Day 22 (Visit 5), these assessments will be rescheduled and completed at the next visit in which steady state is achieved. Comprehensive information on blood sample acquisition, handling and storage are to be found in the study manual. Sample tube labels should include the patient identification number/protocol code, sample number and visit number and will be detailed in the study laboratory manual.

Samples will be stored at -70°C (refer to study manual) at the study center until shipment under appropriate conditions to the analytical laboratory. The analytical laboratory will measure plasma concentrations of BVD-523 using a validated method.

### 6.9.2 Pharmacokinetic Endpoints

Blood BVD-523 and selected metabolite concentration levels will be measured at specified time points (see Section 3.5.3).

Table 6.4 lists the various parameters that will be calculated.

		Day	Cycle 1 y 1 through	n 21	Day	Cycle 2 22 through	n 42	Cycle 3-X 21 day cycles, visit on 1 st day of cycle	
Visit	1 Screening	2 Baseline	3 Tx	4 	5 Tx	6 Tx	7 Tx	8 -X Tx	Final Study Visit/ Early Discontinuation
Visit Day	-28 to -1	$1\pm 0$	$8 \pm 1$	$15 \pm 1$	$22 \pm 1$	$29 \pm 1$	$36 \pm 1$	43 ± 1	
Informed consent	X								
Inclusion/exclusion criteria	X	X	 	T					
Medical history a	X a	X	X	X	X	X	X	X	X
Concurrent medications	X	Х	Х	X	Х	X	X	X	Х
Demography	X								
Measure height (cm)	Х								
Measure weight (kg)	Х	Х			Х			X	Х
Physical examination *	Х	Х	Х	Х	Х	Х	X	X	Х
ECOG	Х	Х	Х	Х	Х	Х	X	X	Х
Vital signs	Х	Х	Х	X	Х	X	X	X	Х
Ophthalmology exam b	Х								Х
Pregnancy test c,d	X	X c			X d			X d	X d
Study drug dispensed		X	X	X	X	X	X	X	
Study drug administration e		Х			Х				
Pharmacokinetic samples f,g		X f,g			X f,g				
Pharmacodynamic samples f,g		X f,g			X f,g				
PBMC samples f,g		X f,g			X f,g				
Assess current disease status**	X				X			X	Х
Bone marrow aspirates and/or $biopsy^h$	X k				X k			X k	$X^k$
Bone marrow cytogenetics h	X k				X k			X k	$X^k$
Clinical lab tests i	Х	Х	Х	Х	Х	Х	Х	X	Х

#### Table 6.3Part 1 and 2: Schedule of Assessments and Procedures

		Da	Cycle 1 y 1 through	21	Day	Cycle 2 22 through	42	Cycle 3-X 21 day cycles, visit on 1 st day of cycle	
Visit	1 Screening	2 Baseline	3 Tx	4 Tx	5 Tx	6 Tx	7 Tx	8 -X Tx	Final Study Visit/ Early Discontinuation
Visit Day	-28 to -1	$1\pm 0$	$8 \pm 1$	$15 \pm 1$	$22 \pm 1$	$29 \pm 1$	$36 \pm 1$	43 ± 1	
Electrocardiogram (ECG) j	Х		Х						
Adverse events (AEs)		Х	Х	Х	Х	Х	Х	Х	Х
Compliance by pill count			Х	Х	Х	Х	Х	Х	Х
Obtain unused drug			Х	Х	Х	Х	Х	Х	Х
ECHO cardiogram or MUGA	Х								

#### Table 6.3Part 1 and 2: Schedule of Assessments and Procedures

Table footnotes:

a Full medical history at screening, review/update of history only at subsequent visits.

b Ophthalmological examinations will be performed by an ophthalmologist at screening, at study termination and if clinically indicated.

c ONLY if the screening serum pregnancy test was performed more than 1 day previously.

d After screening and baseline, urine pregnancy test which if positive, confirm with serum test.

e Study drug to be taken twice daily, first dose in clinic on days when PK sampling occurs i.e., Cycle 1 on Visit 2 (Day 1) and Visit 5 (Day 22), remaining doses on all other days to be self-administered by patient.

f PK blood samples will be collected prior to first morning dose and at 0.5 hours, 1 hour, 2 hours, 4 hours, 6 hours, 8 hours and 12 ±2 hours post-dose. Pharmacodynamic and PBMC blood samples will be collected prior to first morning dose and at 4 hours post-dose.

g Pharmacodynamic, PK, and PBMC blood samples are required at baseline where feasible. Additional biomarkers and DNA sequence analysis may be identified and measured as appropriate by collection of whole blood prior to dosing initiation and after drug levels have reached steady-state. Leukemic cell genotyping by DNA analysis may be performed to identify somatic alterations, relying on either available stored samples or freshly collected samples.

h Bone marrow aspirate and/or biopsy. Peripheral, Geimsa and Iron stained slides to be provided with each bone marrow aspirate or biopsy. Bone marrow cytogenetics (cytogenetics should include at least 20 clones). Bone marrow aspirates may be used to evaluate biomarkers of drug response.

i Chemistry (to include calcium and inorganic phosphorus), hematology and urinalysis. After Cycle 2, clinical chemistry (to include calcium and inorganic phosphorus), hematology and urinalysis may be performed once per cycle or more frequently at the investigator's discretion.

j Patients with a normal ECG in Cycle 1 need not have repeat ECGs in subsequent cycles. Patients should be supine for 5 minutes prior to the ECG.

k Bone marrow aspirates will be obtained at Screening, Cycle 1-Day 22, and every other cycle thereafter. At treatment discontinuation visit, bone marrow aspirates will not be obtained if termination is due to disease progression.

\* Physical examinations should be symptom driven after the Screening Visit.

\*\* Assessments of current disease status will be obtained at Screening, Cycle 1–Day 22, and every other cycle thereafter.

#### Table 6.4Pharmacokinetic Parameters to be Estimated after Dose 1 and at Steady State

C max	Peak plasma concentration determined manually by visual inspection of plasma concentration vs. time figures on the untransformed (linear) scale of measurement
t max	Time to reach the peak plasma concentration determined manually by visual inspection of plasma concentration vs. time figures on the untransformed (linear) scale of measurement
AUC 0-12	Area under the plasma concentration-time curve from 0 to 12 hours post dosing, calculated by linear/log trapezoidal method
AUC 0-last	Area under the plasma concentration-time curve from time 0 to time of last observation after dosing calculated by linear/log trapezoidal method
$\lambda_Z$	Elimination rate constant, determined by linear regression of at least 3 points on the terminal phase of the log-linear plasma concentration- time curve. The correlation coefficient ( $r^2$ ) for the goodness of the fit of the regression line through the data points has to be 0.85 or higher, for the value to be considered reliable. If the WinNonlin data points are not on the linear portion of the terminal slope, the data points will be selected manually prior to calculation of lambda z
t 1/2	Terminal half-life, defined as 0.693 divided by lambda z

# 7 DISCONTINUATION CRITERIA

## 7.1 EARLY DISCONTINUATION OF THE STUDY

It is agreed that for reasonable cause, either the Investigator or the Sponsor may terminate this study, provided a written notice is submitted at a reasonable time in advance of intended termination. If discontinuation is by the investigator, notice is to be submitted to BioMed Valley Discoveries, Inc. If discontinuation is by the Sponsor, notice will be provided to each investigator.

If a severe local reaction or drug-related SAE occurs at any time during the study, the Safety Monitoring Committee will review the case immediately.

The study will be immediately suspended and no additional BVD-523 doses will be administered pending review and discussion of all appropriate study data by the SMC if one or more patients at any dose level develop any of the following adverse events deemed to be possibly, probably or definitely related to BVD-523 by the Investigator and/or Medical Monitor, based upon close temporal relationship or other factors:

- Death
- Anaphylaxis (angioedema, hypotension, shock, bronchospasm, hypoxia, or respiratory distress)

The study will not be restarted until all parties have agreed to the course of action to be taken and the Institutional Review Board/Ethic Committee (IRB/EC) (s) has/have been notified.

## 7.2 DISCONTINUATION OF INDIVIDUAL PATIENTS

Patients are to be withdrawn from the study for any of the following reasons:

- Withdrawal of informed consent
- Disease progression (at the discretion of the PI)
- Unacceptable toxicity
- Changes in the patient's condition which render the patient unacceptable for further treatment in the judgment of the PI
- At least 3 interruptions of BVD-523 intake of > 7 days each, or 8 consecutive days
- Patient becomes pregnant (withdrawal is required)
- Patient is lost to follow-up

Patients will also to be withdrawn at any time if the Investigator concludes that it would be in the patient's best interest for any reason. Protocol violations do not lead to patient withdrawal unless they constitute a significant risk to the patient's safety.

Patients can voluntarily withdraw from the trial for any reason at any time. They are to be considered withdrawn if they state an intention to withdraw, fail to return for visits, became lost to follow up for any reason, or if any of the following occurs:

- Discovery of patient ineligibility
- Significant errors in treatment compliance of at least three interruptions of 7 days each, any treatment interruption of ≥8 consecutive days, or incomplete dosing for greater than 7 days
- Missed / unscheduled / off-schedule / incomplete / incorrect assessments that result in patients being put at risk.

In Part 1 of the study, patients who withdraw at any time due to unrelated AEs preceding the last visit of Cycle 1 (Day 22) will constitute an early discontinuation and must be replaced in order to ensure proper data accrual for dose escalation decisions. A patient who experiences a DLT in Cycle 1 and withdraws before Day 22 either because of the toxicity or otherwise, will nonetheless have that DLT counted in the assessment of potential cohort expansion and/or dose escalation (Table 3.2).

In Part 2 of the study, patients who withdraw at any time preceding the last visit of Cycle 2 (Day 43) will constitute an early discontinuation and will not be replaced and will be evaluated in the Intent to Treat analysis. If patients withdraw due to progressive disease or AEs, replacement of such patients potentially introduces bias into the study. If a patient withdraws for other reasons, replacement of the patient will be decided by the Safety Monitoring Committee.

The investigator must determine the primary reason for a patient's withdrawal from the study and record this information on the eCRF.

# 8 TREATMENT

The safety and PK of BVD-523 will be tested in sequentially increasing doses starting at 300 mg twice daily, initially in patient cohorts of 3 patients (for tabular summary, see Table 3.2). Dose escalations of BVD-523 will occur in 100% increments in cohorts until one patient experiences a study related  $\geq$  Grade 2 toxicity (excluding alopecia or diarrhea), after which dose increases will be  $\leq$  50%. If one patient in a 3 patient cohort experiences a DLT as defined in Table 3.2, up to 3 additional patients will be treated at this dose level. If more than one DLT occurs in  $\leq$  6 patients, this dose level will be defined as the non-tolerated dose and dose escalation will be stopped.

Doses will not be escalated unless the patient(s) receiving the highest current dose have been observed for at least 3 weeks and dose-limiting side effects have been reported in less than 2 of 6 patients assigned to a given dose. Before each escalation, Clinical Investigators will be consulted to ensure that all involved agree with the escalation decision. Once the RP2D has been identified, up to 40 additional patients with pre-defined genetic types will be treated at this dose in Part 2.

Patients experiencing DLT or unacceptable toxicity will have their treatment interrupted until the toxicity returns to  $\leq$  Grade 1 or pre-treatment baseline (whichever is more severe). Resumption of BVD-523 treatment may then be at the next lower dose level where the safety profile has previously been established or between the dose level yielding unacceptable toxicity and the previous dose level, aligning with capsule dose availability.

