## 1.4 PREVIOUS HUMAN EXPERIENCE

This study will be the second study conducted with BVD-523 in humans. The first study, Protocol BVD-523-01, "Phase 1 Dose-escalation, safety, pharmacokinetic and pharmacodynamics study of BVD-523 in patients with advanced malignancies", is in progress. Twenty seven patients with advanced malignancies have been treated in the doseescalation part (Part 1) of the first-in-man Phase 1 clinical study to investigate the safety of BVD-523 and define the MTD and the recommended Phase 2 dose (RP2D). The dose escalation phase included dose levels of 10, 20, 40, 75, 150, 300, 600, 750, and 900 mg b.i.d. The MTD and RP2D of BVD-523 was established to be 600 mg b.i.d (82).

The most common adverse events included diarrhea, nausea, vomiting or constipation (89%), rash (any form), dermatitis, or pruritus (78%), fatigue (70%), decreased appetite (37%), dyspnea (33%), and anemia (26%). Pharmacokinetics were generally linear and dose proportional up to 600 mg twice a day, and BVD-523 achieved pharmacologically relevant exposure (82).

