# 2.1 RATIONALE FOR THE DOSES AND THE DOSING REGIMEN

The human Phase 1 starting dose for BVD-523 in the first trial (BVD-523-01) was derived from 28-day GLP toxicology studies performed in rodent and non-rodent species and calculated as described by Senderowicz (83). Specifically, our results indicated that toxicity in rodents would be used to establish starting dose in patients. The severely toxic dose in 10% of the animals (STD10) for BVD-523 when administered for up to 28 days in Sprague-Dawley rats was determined to be 12.5 mg/kg dosed twice daily (25 mg/kg/day). A standard 10-fold reduction of this dose was scaled to establish a starting dose of 13.5 mg twice-daily of BVD-523 (free base equivalents) or 14.6 mg twice-daily of BVD-523, based on an average body surface area of 1.8 m^2 consistent with current clinical practice and dosing convenience, the proposed starting dose for the first Phase 1 clinical study with BVD-523 in cancer patients (BVD-523-01) was 10 mg twice-daily (20 mg/day) (84).

The starting dose determination for this Phase 1/2 study (BVD-523-02) in AML or MDS patients described herein is based on the clinical experience during the dose-escalation study in patients with solid tumors. The dose escalation phase of study BVD-523-01, the first-in-man Phase 1 clinical study included 27 patients treated at dose levels of 10, 20, 40, 75, 150, 300, 600, 750, and 900 mg b.i.d. DLTs were observed in 5 pts: 2 with grade 3 rash (600 mg and 750 mg b.i.d.), 1 with grade 3 pruritus and elevated AST (900 mg b.i.d.), 1 with grade 3 diarrhea, vomiting, dehydration and elevated creatinine (900 mg b.i.d.), and 1 with grade 2 hypotension, elevated creatinine, and anemia (750 mg b.i.d.); the MTD was established at 600 mg b.i.d. BVD-523 achieved pharmacologically relevant exposure and manageable tolerability at its MTD of 600 mg b.i.d (82). Ex vivo whole blood assays demonstrated inhibition of phosphorylation of RSK, a downstream substrate of the target ERK, at doses  $\geq$  40 mg, b.i.d. Additionally, inhibition of metabolic activity was demonstrated by FDG-PET at 75 mg, b.i.d. The 300 mg b.i.d. starting dose for the BVD-523-02 study with AML or MDS patients is based upon these results in the solid tumor study. As the ongoing Phase 1 study progresses, the 300 mg b.i.d. starting dose in AML or MDS patients may be revised based upon accruing safety experience and determination of the RP2D from the solid tumor study.

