## 3.1.3 Summary of Dose Escalation

#### Table 3.2Summary of Dose Escalation

Observed Safety Outcomes	Action
1 DLT in 3 patients	Expand cohort up to 6 patients
1 DLT in 6 patients	Escalate by $\leq 50\%$ to next dose level
> 1 DLT in $\leq$ 6 patients	Stop dose escalation

*Note*: DLT is defined in detail in Section 3.1.4.2 below.

Each cohort can only begin when the previous cohort has completed treatment to at least the end of Cycle 1 without fulfilling a criterion which would prevent dose escalation. Intra-patient dose escalation will be permitted with consensus among the Principal Investigator, Medical Monitor, and Sponsor, to a dose not to exceed that for which 21 days of treatment has been deemed safe.

Although dose escalation decisions will be taken upon review of the data from Cycle 1, safety data will also be collected from all patients continuing treatment and these data will be reviewed periodically by the Safety Monitoring Committee. Any detected cumulative toxicity may require later dose reductions or other action as appropriate, including having an effect on the RP2D.

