#### **DLTs**

For this study, Dose Limiting Toxicities (DLTs) are based upon the first Cycle (first 21 days of treatment), defined as (where Grade refers to CTCAE v 4.0 categorization):

- Any treatment-emergent study drug related Grade 3 or Grade 4 non-hematologic toxicity unless clearly and incontrovertibly unrelated to BVD-523. Exceptions are Grade 3 or 4 nausea or vomiting that is controllable by anti-emetics or Grade 3 or 4 diarrhea controllable by optimal therapy such as loperamide. Grade 3 laboratory investigations other than serum creatinine, bilirubin, AST or ALT will not be considered a DLT unless they are associated with clinical manifestations.
- Study-drug related Grade 4 thrombocytopenia that was not present at study entry and that does not resolve within 7 days, unless clearly and incontrovertibly unrelated to BVD-523.
- Febrile neutropenia or Grade 4 neutropenia that was not present at study entry and that does not resolve within 7 days, unless clearly and incontrovertibly unrelated to BVD-523.
- Prolonged myelosuppression or pancytopenia with a hypocellular bone marrow and no marrow blasts lasting for 6 weeks that is not related to disease progression.
- Any study drug related toxicity that results in treatment delays of > 4 days, except when subject is experiencing rash in which case, subject may be off drug for up to 7 days while receiving treatment.

All subjects who are not evaluable for toxicity in Cycle 1 due to unrelated AEs will be replaced.

Dose escalation will proceed according to the following rules:

Observed Safety Outcomes	Action
1 DLT in 3 subjects	Expand cohort up to 6 subjects
1 DLT in 6 subjects	Escalate by $\leq 50\%$ to next dose level
> 1 DLT in ≤ 6 subjects	Stop dose escalation

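### Protocol Section 8 lets the dose double past the known 600 mg MTD, and after a diarrhea-only DLT it contradicts Table 3.2: a minor text correction

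*Protocol*

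**What the plan says.** Part 1 starts at 300 mg b.i.d. in cohorts of three. Protocol Section 8 gives the size of each step: "Dose escalations of BVD-523 will occur in 100% increments in cohorts until one patient experiences a study related" toxicity of Grade 2 or worse, not counting alopecia or diarrhea. From then on, steps are at most 50%. The section names no dose at which doubling stops. It adds a procedural check: "Before each escalation, Clinical Investigators will be consulted to ensure that all involved agree with the escalation decision".

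Table 3.2 (Protocol Section 3.1.3) gives a step size after a DLT. Its row "1 DLT in 6 patients" allows at most 50%, whatever the type of DLT. The SAP repeats this in Section 3.1 under "1 DLT in 6 subjects".

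Protocol Section 3.1.4.2 exempts Grade 3 or 4 diarrhea from being a DLT only when therapy can control it. It also counts as a DLT any related toxicity that delays treatment by more than 4 days (with a longer allowance for rash), and sets no minimum grade.

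The first study is described in Protocol Sections 1.4 and 2.1: "The dose escalation phase included dose levels of 10, 20, 40, 75, 150, 300, 600, 750, and 900 mg b.i.d", with an MTD of 600 mg b.i.d.

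**The concern.** The protocol had the first study's results when it set this rule. Section 2.1 uses them to choose the starting dose and lets them revise it, but nothing carries them into the step size. The written default from a clean 600 mg cohort is therefore a dose that the first study never gave, above two levels at which it saw DLTs.

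The second problem is internal. The event that ends doubling in Section 8 is not the same as a DLT. Some events that count as DLTs do not end doubling, so two parts of the protocol can prescribe different next doses from the same cohort result. A dosing rule should give one answer.

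**Working it through.** **First-study benchmark.** Section 2.1 lists five DLT patients: 1 at 600 mg (rash), 2 at 750 mg (one rash; one hypotension, creatinine and anemia) and 2 at 900 mg (one pruritus and AST; "1 with grade 3 diarrhea, vomiting, dehydration and elevated creatinine (900 mg b.i.d" for the other). The sum is 1 + 2 + 2 = 5, as stated, and 600 mg is the highest level with at most one DLT patient. This agrees with the stated MTD. Numbers treated per level are not given, so rates cannot be checked.

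**Doubling without a trigger.**
- 300 × 2 = 600 mg; 600 × 2 = 1200 mg.
- 1200 / 600 = 2.0 times the MTD; 1200 / 900 = 1.33 times the highest dose given.
- With a 50% limit, 600 × 1.5 = 900 mg.

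This path needs no trigger event in 3 + 3 = 6 patients, with chance (1 − p)^6, where p is the per-patient chance of a related Grade 2 or worse toxicity other than alopecia or diarrhea. The documents do not give p. Over an assumed range:

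| p | (1 − p)^6 |
|---|---|
| 0.20 | 26% |
| 0.30 | 12% |
| 0.50 | 1.6% |
| 0.70 | 0.07% |
| 0.78 | 0.01% |

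The last two rows borrow the first study's all-grade frequencies for fatigue (70%) and for rash, dermatitis or pruritus (78%) in Section 1.4. They assume that every such patient had a related event of Grade 2 or worse, which the documents do not say.

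**Conflict with Table 3.2.** Two kinds of DLT fail to end doubling under Section 8:
- diarrhea alone, either uncontrolled Grade 3 or 4 or, if related, any grade that delays dosing by more than 4 days;
- a related Grade 1 event that causes such a delay.

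Suppose that is the single DLT in six and no other trigger has occurred.
- At 300 mg: Section 8 gives 300 × 2 = 600 mg; Table 3.2 gives at most 300 × 1.5 = 450 mg. The 5 other patients must be trigger-free: 0.7^5 = 17% at p = 0.30, 0.5^5 = 3% at p = 0.50.
- At 600 mg: 1200 mg against at most 900 mg. The 3 patients at 300 mg and 5 others at 600 mg must be trigger-free: 0.7^8 = 6%, 0.5^8 = 0.4%.

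These are then multiplied by the chance of such a DLT, for which there is no figure. As an illustration at 300 mg, assume 4% per patient. The DLT must fall among the first three, so 3 × 0.04 × 0.168 = 2% at p = 0.30 and 3 × 0.04 × 0.031 = 0.4% at p = 0.50. Both are slightly high, because the factor for no second such DLT is left out.

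**The case against.** The strongest reply is that Table 3.2 already governs. Protocol Section 7.2 cites it when saying how a DLT counts toward expansion and escalation, and Section 8 refers to it as its tabular summary. A specific, stricter row would naturally prevail over a general default. This makes the safer reading the likelier one, but Section 8 does not say that the table overrides its own step size.

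The triggering cases are also rare, and that stands. Sections 8 and 8.1.2 let dosing resume at Grade 1, so a Grade 1 event would seldom hold treatment; only a vision change requires a stop regardless of grade (Section 6.5). None of the first study's five DLT patients had diarrhea alone. If the listed grade covers each event named, all five would have ended doubling.

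On the absence of a limit, finding an MTD in AML or MDS is a primary objective, so the solid-tumor MTD need not be a ceiling. Section 3.3 requires a safety review before each new level, all involved must agree, and Section 3.1.2 allows intermediate doses, including after a large step has proved intolerable. Section 3.1.4.2 also presumes toxicities related unless definitively explained otherwise; if that presumption extends to Section 8, which is not stated, doubling would end sooner. These controls could well have stopped a step to 1200 mg, but none states a dose limit. The objection supports a smaller step rather than a fixed ceiling.

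A reader might also count the lack of a row for no DLT in three patients as a further error. It is not one: Section 8 supplies that step in its text.

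**Conclusion.** The point holds as a minor correction. The written rule permits a default step to twice a known MTD, and for a narrow class of DLTs it disagrees with Table 3.2 and its SAP copy by 150 mg at the first step (600 against 450) or 300 mg at the second (1200 against 900). Both routes are improbable at plausible trigger rates, but every probability here rests on an assumed rate.

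The severity is low because SAP Section 5.2 names 600 mg as the RP2D and SAP Section 15 describes a revision for Part 2, so the rule has little remaining use. The only cohort-level dose revision described for Part 2 (Protocol Section 10.1.2) is downward. No endpoint or analysis depends on it.

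A reader might infer that patients received 1200 mg, or that the 600 mg RP2D was reached by a faulty step. The documents support neither. They do not say which levels were opened, and a plan is not expected to; SAP Section 5.2 already provides for Part 1 safety results by dose level.

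**What to change.** Add two sentences to Protocol Section 8:

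1. After any DLT of any type, including diarrhea, Table 3.2 governs and the next step is at most 50%.
2. Every step from 600 mg b.i.d. upward is at most 50%.

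The second sentence still permits 900 mg directly from 600 mg, a level with two DLT patients in the first study. The text should therefore ask that 750 mg (750 / 600 = 1.25, a 25% step) be considered first.

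The cost is wording only, with no change to any analysis and no extra patients for a completed Part 1. If the rule were applied again, the downside is possibly one extra intermediate cohort of 3 to 6 patients.
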